4.1 Inclusion criteria

1. Patients with multiple myeloma who demonstrate evidence of serologic relapse/progression while on lenalidomide maintenance given as part of **first** line therapy (including upfront high-dose chemotherapy followed by autologous hematopoietic cell transplantation (HCT)) without symptomatic relapse/progression.

Lenalidomide maintenance is defined as **single agent** lenalidomide therapy of any doses up to 15 mg PO daily for 14-28 days (28-day cycle). Relapse/progression is defined as increase of 25% from lowest confirmed response value in one or more of the following criteria: Serum M –protein (absolute increase must be ≥ 0.5 g/dl)

Serum M-protein increase >1 g/dl, if the lowest M component was >5 g/dl

Urine M –protein (absolute increase must be > 200 mg in 24 hours)

In patients without measurable serum and urine M-protein levels, the difference between involved and uninvolved FLC levels (absolute increase must be > 10 mg/dl)

For patients relapsing from complete remission, relapse is defined as:

Reappearance of serum or serum M-protein by immunofixation or electrophoresis.

2. Male or female patients aged ≥ 18 years old

3. Ability to provide written informed consent obtained prior to participation in the study and any related procedures being performed

4. Measurable disease with at least 1 of the following assessed within 28 days prior to Cycle 1 Day 1:

A. Serum M-protein ≥ 0.5 g/dL,

B. Urine M-protein ≥ 200 mg/24 hour,

C. In subjects without measurable serum or urine M-protein, serum free light chain (SFLC) > 10 mg/dL (involved light chain) and an abnormal serum kappa lambda ratio

5. Patients must meet the following laboratory criteria within 28 days prior to Cycle 1, day 1:

- Absolute neutrophil count (ANC) $\geq 1 \times 10^9/L$
- Hemoglobin $\geq 10 \text{ g/dL}$
- Platelet count $\geq 75,000/\text{mm}^3$
- AST and ALT $\leq 2.5 \times \text{ULN}$
- Serum bilirubin $\leq 1.5 \times \text{ULN}$
- Serum Creatinine clearance $\geq 50\text{ml}/\text{min}$

4.2 Exclusion criteria

1. Prior Elotuzumab
2. Patients with clinical relapse/progression as per the IMWG uniform criteria defined as one or more of the following criteria:
 - A. Development of new soft tissue plasmacytomas or bone lesions (osteoporotic fractures do not constitute progression)
 - B. Definite increase in the size of existing plasmacytomas or bone lesions. A definite increase is defined as a 50% (and $\geq 1 \text{ cm}$) increase as measured serially of the measurable lesion
 - C. Hypercalcemia ($>11 \text{ mg/dL}$);
 - D. Decrease in hemoglobin of $\geq 2 \text{ g/dL}$ not related to therapy or other non-myeloma-related conditions;
 - E. Rise in serum creatinine by 2 mg/dL or more from the start of the therapy and attributable to myeloma
 - F. Hyperviscosity related to serum paraprotein
3. Women who are pregnant or breast feeding or women of childbearing potential (WOCBP) not using an effective method of birth control. WOCBP are defined as sexually mature women who have not undergone a hysterectomy or who have not been naturally postmenopausal for at least 12 consecutive months (i.e., who has had menses any time in the preceding 12 consecutive months). Women of childbearing potential must have a negative serum pregnancy testing within 7 days prior to the administration of drug.

4. Male patients whose sexual partners are WOCBP not using effective birth control
5. Patients with a prior malignancy within the last 5 years (except for skin basal or squamous cell carcinoma, or *in situ* cancer of the cervix)
6. Patients with known positivity for human immunodeficiency virus (HIV) or hepatitis C; baseline testing for HIV and hepatitis C is not required
7. Patients with a diagnosis of POEMS syndrome (polyneuropathy, organomegaly, endocrinopathy, monoclonal protein, and skin changes) or plasma cell leukemia ($> 2.0 \times 10^9/L$ circulating plasma cells by standard differential)

5 Treatments

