5.5 Lenalidomide

Lenalidomide will be taken once-daily by mouth days 1-21 of each cycle at 25 or 10 mg daily depending on the treatment cohort to whom the subject is randomized to, with or without food. Lenalidomide capsules should be swallowed whole with water. The capsules should not be opened, broken, or chewed. Subjects will be instructed to take the lenalidomide dose at approximately the same time every day. If a planned administration of lenalidomide is missed, it should be taken as soon as possible within the same calendar day with a return to schedule the following day. If a calendar day of dosing is missed, subjects should not make up doses, but should resume the dosing regimen on schedule with the next course. Missed doses must be reported.

For female subjects of childbearing potential, non-pregnant state must be documented prior to the first dose of lenalidomide, and prior to the start of each subsequent cycle.

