5.10.1.1 Required Concomitant medications

Pre-medications on days that Elotuzumab is administered

Dexamethasone- 28 mg PO 3-24 hours prior to Elotuzumab dose

Dexamethasone 8 mg IV 45-90 min prior to Elotuzumab dose

H₁blocker; diphenhydramine (25-50 mg PO/IV) 45-90 min prior to Elotuzumab dose

H₂blocker; Ranitidine or equivalent H₂ blocker (50 mg IV or 150 mg PO), 45-90 min prior to Elotuzumab dose

Acetaminophen 650-1000 mg PO 45-90 min prior to Elotuzumab dose

Anticoagulant Prophylaxis

Aspirin (or other anticoagulant or antiplatelet medication such as clopidogrel bisulfate, low-molecular-weight heparin, or warfarin or factor X inhibitors), is a required concomitant medication while taking lenalidomide. In subjects with a prior history of deep vein thrombosis, low-molecular-weight heparin or therapeutic doses of warfarin (for a target international normalized ratio of 2–3) are required. Enteric-coated aspirin once-daily by mouth at the standard prophylactic dose should be administered for the duration of treatment with lenalidomide. Subjects with known high thrombotic risk, e.g., prior deep vein thrombosis, should receive full anticoagulation at the investigator's discretion

Contraception

Females of childbearing potential (FCBP) must:

- Avoid pregnancy for at least 4 weeks before beginning lenalidomide
- Have a negative pregnancy test within 7 days prior to starting treatment, and each subsequent cycle.
- Pregnancy tests monthly during treatment after the first month or semimonthly for women of childbearing potential with irregular menstruation
- Agree to abstain from heterosexual sexual intercourse or to use 2 methods of effective contraception beginning 4 weeks prior to initiating treatment with lenalidomide, during therapy, during dose interruptions and for 3 months following last dose of drug (more frequent pregnancy tests may be conducted if required per local regulations) An FCBP is defined as a sexually mature female who: 1) has not undergone a hysterectomy or bilateral oophorectomy, or 2) has not been naturally postmenopausal for at least 24 consecutive months (i.e., no menses at any time in the preceding 24 consecutive months). Amenorrhea following cancer therapy does not rule out childbearing potential.

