6.3.4 Laboratory evaluations

Laboratory evaluation should be done at screening (within 28 days of cycle 1, day 1), and on day 1 of each treatment cycle. Results must be reviewed prior to administering Elotuzumab. More frequent examinations may be performed if medically indicated; results should be recorded.

Hematology

Hematology must include hemoglobin, hematocrit, platelets, total white blood cell count (WBC) and differential.

Blood chemistry

Biochemistry includes the following parameters: BUN, creatinine, sodium, potassium, chloride, CO_2 (HCO_3), glucose, calcium, albumin, total protein, total bilirubin, alkaline phosphatase, AST/SGOT, ALT/SGPT. If total bilirubin is greater than the upper limit of normal, direct and indirect bilirubin should be performed.

Serum pregnancy test

All females of childbearing potential should complete a serum pregnancy test within 7 days prior to the administration of Elotuzumab and lenalidomide on day 1 of cycle 1. The pregnancy test should be repeated in week 1 of every cycle (except for cycle 1). Postmenopausal women must have been amenorrheic for ≥ 12 months in order to be considered "of non-childbearing potential".

Performance status

Performance status will be assessed by ECOG performance status scale.

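### Childbearing potential ends at 12 months postmenopausal in four places but at 24 in section 5.10.1.1, and the repeat pregnancy test is timed more loosely in 6.3.4 than in 5.5

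*Combined protocol and SAP*

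**What the plan says.** **Who counts as of childbearing potential.** Section 4.2, item 3 (repeated in the synopsis) excludes "Women who are pregnant or breast feeding or women of childbearing potential (WOCBP) not using an effective method of birth control". It counts women without a hysterectomy, or who "have not been naturally postmenopausal for at least 12 consecutive months". Section 6.3.4, with identical words in the pregnancy-test footnote to Table 6-1, says "Postmenopausal women must have been amenorrheic for ≥ 12 months in order to be considered" no longer of childbearing potential. Section 5.10.1.1 counts a woman who "has not been naturally postmenopausal for at least 24 consecutive months" and adds: "Amenorrhea following cancer therapy does not rule out childbearing potential".

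**When the test is repeated.** Section 6.3.4 and the footnote: "The pregnancy test should be repeated in week 1 of every cycle (except for cycle 1"). Section 5.5, for women of childbearing potential: "non-pregnant state must be documented prior to the first dose of lenalidomide, and prior to the start of each subsequent cycle". Section 5.10.1.1: "Have a negative pregnancy test within 7 days prior to starting treatment, and each subsequent cycle"; it also asks for monthly tests after the first month, or semimonthly tests where menstruation is irregular. The synopsis, Table 6-1 and the opening of 6.3.4 schedule testing on day 1 of each cycle. The opening of 6.3.4 also requires results to be reviewed before elotuzumab is given, and does not mention lenalidomide.

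**Contraception.** Exclusion 3 asks women for one effective method. Section 5.10.1.1 asks for abstinence or two methods, starting 4 weeks before lenalidomide. Section 5.1 requires the Prescribing Information's precautions on pregnancy testing and contraception to be followed whenever lenalidomide is dispensed or given.

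**The concern.** Section 5.1 describes lenalidomide as a thalidomide analogue, so the pregnancy rules are a real safeguard, and sites need one answer on who is tested and when. Two features of the text work against that.

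First, the same woman is of childbearing potential in one section and not in others. The shorter threshold sits in the eligibility list and the visit table, the places that staff are most likely to work from. The longer one sits under concomitant medications. The caution about amenorrhea after cancer therapy appears only there, although entrants have had first-line myeloma therapy, which may include high-dose chemotherapy with autologous transplant (4.1, item 1).

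Second, a site that schedules by 6.3.4 or the footnote alone could take the sample after that cycle's lenalidomide has begun.

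At stake are missed tests, avoidable protocol deviations and uneven practice between patients. The efficacy analysis is not involved.

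**Working it through.** The plan gives no figure to reproduce. The check is a side-by-side reading with two small counts.

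| Place | Childbearing potential ends at | Pregnancy test rule |
|---|---|---|
| Synopsis and 4.2, item 3 | 12 months | Negative serum test within 7 days before drug (entry) |
| 6.3.4 and Table 6-1 footnote | 12 months | Same at entry; then week 1 of each cycle from cycle 2 |
| 5.5 | Not defined | Before the first dose and before each later cycle starts |
| 5.10.1.1 | 24 months, with the amenorrhea caution | Within 7 days before treatment and each cycle; monthly, or semimonthly if irregular |

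**Step 1, definition.** The band classified differently is 24 − 12 = 12 months wide: women 12 to 23 completed months postmenopausal. Take a woman at 18 months.

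- Under 4.2 she is not of childbearing potential, so exclusion 3 asks nothing of her on contraception. Under 6.3.4 she needs no test.
- Under 5.10.1.1 she is of childbearing potential, so she needs a test each cycle and abstinence or two methods.
- Scheduling on day 1 does not resolve this. The synopsis lists the test only where applicable, and 5.5 covers women of childbearing potential without defining them. Both depend on the definition in dispute.

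**Step 2, timing.** Lenalidomide is taken daily on days 1 to 21. A sample on day k, before that day's dose, follows k − 1 doses of the cycle.

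- Day 1: 0 doses.
- Day 4: 3 doses.
- Day 7: 6 doses, and 6/21 = 28.6% of the cycle's doses.

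A test on days 2 to 7 therefore meets 6.3.4 but not 5.5. A day 1 test before the dose meets 6.3.4, 5.5 and the each-cycle test in 5.10.1.1. With day 1 testing scheduled, 0 doses is the expected case. These are counts of doses, not estimates of risk.

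**Step 3, results review.** The sentence in 6.3.4 holds back elotuzumab until results are seen. It does not hold back the lenalidomide capsule, the drug for which 5.5 sets its pregnancy requirement.

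**Step 4, contraception.** A woman who meets 5.10.1.1 by using two methods also meets exclusion 3. A woman on one method passes exclusion 3 but does not meet 5.10.1.1. This is a weaker entry rule beside a stricter binding rule, and both can be met together. One point is open: patients enter while already on lenalidomide maintenance (4.1, item 1), and 5.10.1.1 does not say whether its 4 weeks precede that earlier start or cycle 1 day 1.

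**The case against.** The strongest reply is that nothing unsafe is allowed. Sections 5.5 and 5.10.1.1 are requirements, 5.1 brings in the Prescribing Information, and day 1 testing is on the schedule. A site that always followed the stricter text would break no section. On this view the matter is housekeeping.

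Most of that stands. A reader might infer from the week 1 wording that the protocol lets a cycle start without a pregnancy test. It does not: 5.5 forbids it, and such a start would be a deviation. A reader might also see the contraception texts as a conflict. They are not, because the entry rule and the stricter rule are compatible.

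The reply does not remove the definitional contradiction. Two sections classify the same woman in opposite ways, and the protocol does not rank them. The general reference in 5.1 leaves the 12-month text in place in four locations.

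A reader might further infer that exclusion 4, on male patients, should be rewritten to carry the male rule of 5.10.1.1. The documents do not support that. Exclusion 4 is limited to men with partners of childbearing potential. Section 5.10.1.1 asks men for one highly effective plus one additional method, even after vasectomy, without stating partner scope or an abstinence option. Importing that rule as an entry bar would exclude a man with a postmenopausal partner unless he agreed to two methods. That changes eligibility and is not a wording repair.

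**Conclusion.** The point holds as an internal inconsistency of low severity. The 12 against 24 month definition is a direct contradiction affecting a 12-month band of women. The week 1 wording is looser than 5.5 but can be reconciled with it by a pre-dose day 1 test. Exclusion 3 is weaker than 5.10.1.1 without conflicting with it.

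There is no effect on endpoints, sample size or power. The documents do not say how many women fall in the band; that the number is small is an assumption. The case for acting is that the contradiction is plain, the subject is a pregnancy safeguard, and the correction is brief.

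**What to change.** In one amendment:

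- (a) Use the 24-month definition of 5.10.1.1, with its sentence on amenorrhea after cancer therapy, in the synopsis, 4.2, 6.3.4 and the Table 6-1 footnote.
- (b) In 6.3.4 and the footnote, replace the week 1 wording with: *negative result documented within 7 days before the day 1 lenalidomide dose of every cycle, and semimonthly for irregular menstruation as in 5.10.1.1*.
- (c) Extend the review sentence in 6.3.4 to cover starting lenalidomide as well as giving elotuzumab.
- (d) Have exclusion 3 refer to the female contraception rule of 5.10.1.1, keeping its pregnancy, breast-feeding and 7-day serum test wording. The sponsor should state which lenalidomide start the 4 weeks precede.

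Leave exclusion 4 limited to men with partners of childbearing potential. Clarify partner scope and abstinence for men within 5.10.1.1.

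**Cost.** A few more women are tested each cycle, as 5.10.1.1 already requires, and a cycle may occasionally wait briefly for a result. The 5.10.1.1 definition also releases women after bilateral oophorectomy, whom 4.2 does not name. Item (d) has a conditional cost. If the sponsor counts the 4 weeks from cycle 1 day 1, a woman not already meeting the rule could wait up to 28 days. A screening test done j days before she began to meet it would then be 28 + j days old, outside the 28-day window for any j above 0, so some screening might be repeated. If the sponsor counts from the original lenalidomide start, that wait does not arise.

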5.1 Investigational therapy

Elotuzumab will be provided by BMS as investigational product. Elotuzumab (BMS-901608, also known as HuLuc63) is an immune-stimulatory humanized, IgG1 monoclonal antibody (mAb) targeted against signaling lymphocyte activation molecule family 7 (SLAMF7), a glycoprotein expressed on myeloma and natural killer (NK) cells. EMPLICITI™ (Elotuzumab) is commercially available and is indicated in combination with lenalidomide and dexamethasone for the treatment of patients with multiple myeloma who have received one to three prior therapies. All precautions and restrictions included in the Prescribing Information (e.g., pregnancy testing and contraception) must be observed when dispensing and administering lenalidomide as part of this protocol. During the study, Elotuzumab will be administered in combination with lenalidomide at a dose of 10 mg/kg administered intravenously every week for the first two cycles and at a dose of 20 mg/kg monthly thereafter until disease progression or unacceptable toxicity.

Product Description / Class and Dosage Form	Potency	IMP/NonIMP	Blinded or Open Label	Packaging / Appearance	Storage Conditions (per label)
Elotuzumab Powder for Solution for Infusion	400 or 300 mg/vial	IMP	Open Label	Vial	Refer to the label on container

Lenalidomide is a thalidomide analogue indicated for the treatment of subjects with multiple myeloma, in combination with dexamethasone, in subjects who have received at least 1 prior therapy.

Lenalidomide is a commercially available drug, available for oral administration, depending upon local health authority approvals ([Celgene Corporation 2013](#)).

All precautions and restrictions included in the Prescribing Information (e.g., pregnancy testing and contraception) must be observed when dispensing and administering lenalidomide as part of this protocol.

During the study lenalidomide will be administered at 10 or 25 mg PO daily days 1-21 of 28 days cycles until disease progression or discontinuation.

Dexamethasone is a commercially available drug. The description, how supplied, and storage instructions for dexamethasone product are found in the prescribing information.

During the study dexamethasone will be administered as premedication for Elotuzumab as indicated in the package insert.

Treatment assignment

Patients will be randomized to either (1) cohort A = lenalidomide 25 mg PO daily days 1-21 or (2) cohort B = lenalidomide 10 mg PO daily days 1-21 with Elotuzumab.

5.2 Treatment cycle and duration

Treatment cycles will have a duration of 28 days and subjects will receive Elotuzumab on days 1,8,15, and 22 of cycles 1-2 and on day 1 on cycle 3 and beyond, in combination with lenalidomide at either 25 mg (cohort A) or 10 mg (cohort B) on days 1-21. All cycles will start 28 days (\pm 3) after the start of the prior cycle.

Subjects will continue therapy until one of the following:

1. Disease progression
2. Withdrawal from the study for any reason
3. Death

5.3 Study Treatment Administration

Cycles 1-2

Elotuzumab/lenalidomide will be given in 28-day cycles:

·Elotuzumab will be administered at a dose of 10 mg/kg weekly IV on Days 1, 8, 15, and 22

·Lenalidomide will be administered at a dose of 25(cohort A) or 10 mg (cohort B) once-daily by mouth on Days 1–21

Day	1	8	15	22	28
Elotuzumab	X	X	X	X	
Lenalidomide					

Cycles 3 and beyond**Elotuzumab/lenalidomide will be given in 28-day cycles:**

·Elotuzumab will be administered at a dose of 20 mg/kg monthly IV on Days 1

·Lenalidomide will be administered at a dose of 25(cohort A) or 10 mg (cohort B) once-daily by mouth on Days 1–21

Days	1	8	15	22	28
Elotuzumab		X			Lenalidomide

Based on the emerging data on accelerated infusion, the infusion rate of Elotuzumab will be at 0.5 mL/min for the first 30 minutes, 1 mL/min from 30 to 60 minutes, then 2 mL/min from 60 minutes and beyond on cycle 1 day 1. On cycle 1 day 8, infusion rate will be 3 mL/min for the first 30 minutes, then 4 mL/min from 30 minutes and beyond. Infusion rate will be 5 mL/min from cycle 1 day 15 and after. All patients will receive pre-medication with antihistamine (25 – 50 mg of diphenhydramine PO or IV), H2 blocker (such as ranitidine 50 mg IV or 150 mg PO or equivalent) and acetaminophen (650 – 1000 mg) PO for potential infusion reactions. As part of pre-medication, dexamethasone 28 mg PO will be given between 3 and 24 hours before Elotuzumab and 8 mg IV between 45 and 90 minutes before Elotuzumab as prescribed in the package insert.

5.4 Elotuzumab

Elotuzumab will be administered intravenously on days 1, 8, 15, and 22 during the first 2 cycles, then on day 1 of each cycle starting third cycle. Based on the emerging data on accelerated infusion, the infusion rate of Elotuzumab will be at 0.5 mL/min for the first 30 minutes, 1 mL/min from 30 to 60 minutes, then 2 mL/min from 60 minutes and beyond on cycle 1 day 1. On cycle 1 day 8, infusion rate will be 3 mL/min for the first 30 minutes, then 4 mL/min from 30 minutes and beyond. Infusion rate will be 5 mL/min from cycle 1 day 15 and after. All patients will receive pre-medication with antihistamine (25 – 50 mg of diphenhydramine PO or IV), H2 blocker (such as ranitidine 50 mg IV or 150 mg PO or equivalent) and acetaminophen (650 – 1000 mg) PO for potential infusion reactions. As part of pre-medication, dexamethasone 28 mg PO will be given between 3 and 24 hours before Elotuzumab and 8 mg IV between 45 and 90 minutes before Elotuzumab as prescribed in the package insert.

5.5 Lenalidomide

Lenalidomide will be taken once-daily by mouth days 1-21 of each cycle at 25 or 10 mg daily depending on the treatment cohort to whom the subject is randomized to, with or without food. Lenalidomide capsules should be swallowed whole with water. The capsules should not be opened, broken, or chewed. Subjects will be instructed to take the lenalidomide dose at approximately the same time every day. If a planned administration of lenalidomide is missed, it should be taken as soon as possible within the same calendar day with a return to schedule the following day. If a calendar day of dosing is missed, subjects should not make up doses, but should resume the dosing regimen on schedule with the next course. Missed doses must be reported.

For female subjects of childbearing potential, non-pregnant state must be documented prior to the first dose of lenalidomide, and prior to the start of each subsequent cycle.

